6.3 Duration of Participation

The duration of each study period will be five consecutive days, and each participant will be asked to complete three of these 5-day periods. During study days, each meal and snack will take approximately 30 minutes to complete. The estimated time required by the participant each day is 2.5 hour for meals. The estimated total time required for all of the meals is 37.5 hours across 15 days. The height and weight measurements and the

Tasting Game on the final visit will require an additional hour of time. For the parents, 30 minutes will be required to complete the questionnaires. The total time commitment for the study is 39 hours.

Teachers will spend approximately 20 minutes per questionnaire.

7.0 Data and Specimen Banking For Future Undetermined Research

7.1 Data and/or specimens being stored

N/A

7.2 Location of storage

N/A

7.3 Duration of storage

N/A

7.4 Access to data and/or specimens

N/A

7.5 Procedures to release data or specimens

N/A

7.6 Process for returning results

N/A

8.0 Statistical Plan

8.1 Sample size determination

The sample size for the study was estimated from a linear mixed model and an approximation technique [5] using exemplary data sets based on prior 1- and 2-day studies in preschool children [2,3]. We assessed the required sample size for several scenarios with different assumptions about changes in intake on days 3 to 5 that represented quadratic trajectories over time. To detect a clinically significant change of 50 kcal/d over time (movement toward adjustment after 3 to 5 days) with a Type 1 error rate of 5% and power of 90%, it was determined that 45 participants would be required. To allow for withdrawals and non-compliance to the protocol, at least 55 children will be enrolled.

8.2 Statistical methods

The main outcomes of the study are daily consumption (by weight, ED, and energy) of manipulated foods, non-manipulated foods and milk, and their combined total. Other outcomes are cumulative intake for the entire 5 days, daily macronutrient intake, daily intake of non-manipulated items by meal component (fruits and vegetables at main meals, grain-based snacks, dairy snacks, fruit and vegetable snacks, and milk), and

physical activity time (daily step counts, sedentary time, and moderate-to-vigorous time). To analyze differences in mean daily outcomes across the 3 experimental conditions, linear mixed models with repeated measures are used. The fixed factors in the models are ED condition (lower-ED, baseline-ED, or higher-ED), study week, study day, menu, classroom, and sex. Interactions between these factors are tested and removed from the model if not significant. Participants are treated as a random effect. The Tukey-Kramer method is used to adjust for multiple pairwise comparisons between means. In order to evaluate the contribution to children's intakes of non-study foods reported by parents, the energy content of the reported items is estimated by study staff. The outcome of daily energy intake is analyzed both with and without the non-study items. This estimated data is not included in further analyses, because these estimates are based on parental recall and were less accurate than measured intake.

Random coefficients models are used to test whether the trajectories of daily intake in the 3 conditions converge over the 5 days, i.e., whether regulation of energy intake occurs over time in response to ED variations. The trajectories of intake over time are modeled separately for each child and allowed to vary randomly. Time (study day) is treated as a continuous covariate in the model and polynomial factors of time (linear and quadratic coefficients) are tested as both fixed and random effects to determine the shape of the intake trajectory. The intercept of the trajectory reflects the magnitude of daily intake. The linear coefficient represents the rate of change in intake (slope) across time after Day 1, and the quadratic coefficient represents the rate of acceleration or deceleration in intake (curvature) across time after Day 1.

The influence of continuous participant characteristics (age, body weight, height, BMI-for-age percentile, BMI z-score, step counts, and questionnaire subscales) on the relationship between the experimental factors and intake is assessed by analysis of covariance with linear mixed models. Because multiple participant characteristics are tested as covariates, the method of Benjamini and Hochberg [6] is used to adjust the significance levels, with the false discovery rate set at 0.05 [6]. In order to standardize for energy needs, models having significant covariance with weight status are adjusted for estimated energy requirements [7]. Differences in subject characteristics between boys and girls, as well as differences in intake between children with and without obesity (sex-specific BMI-for-age percentile ≥ 85 and < 85 , respectively), are assessed by independent-samples t-tests. Within conditions, the means of daily energy intakes expressed as a percentage of estimated energy requirements are compared to 100% using a one-sample t-test and controlling the family-wise error rate using the Bonferroni correction.

It has been predetermined that children who have incomplete intake measures on ≥ 3 days in all 3 conditions will be excluded from analysis. It has also been predetermined that children who eat $> 95\%$ of the food weight served on at least 1 day will be classified as "plate cleaners", and their influence on the results will be tested. To evaluate whether the distribution of taste ratings (yummy, just okay, yucky) of the lunch and snack dishes differs significantly across experimental conditions, ordinal logistic regression is used; results are reported as odds ratios (OR) with 95% confidence intervals. Outcomes from

statistical models are reported as mean \pm SEM and subject characteristics are reported as mean \pm SD. Standardized effect sizes are calculated using Cohen's d statistic, with no adjustment for correlation due to repeated measures. Results are considered significant at $P < .05$. All data are analyzed using SAS software (SAS 9.4, SAS Institute, Inc., Cary, North Carolina, USA).

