1.0 Objectives

1.1 Study Objectives

Aim: To determine the effect of varying the energy density of foods served over five days on energy intake in preschool children.

Hypotheses:

1. Mean daily energy intake will be greater when children are served higher-energy-dense versions of foods over five days than when they are served lower-energy-dense versions of the same foods over five days.
2. Daily energy intake in the conditions with higher and lower energy density will begin to converge across the 5-day period.
3. Energy intake across the 5-day period will be adjusted closer to baseline in response to decreases in energy intake than in response to increases in energy intake.

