1.2 Primary Study Endpoints

1. Daily intake of food and beverages by energy (kilocalories)

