6.0 Study Design and Procedures

6.1 Study Design

This crossover study has a within-subjects design. There will be three experimental conditions; one condition in which meals of lower energy density (ED) are served, one condition in which meals of baseline energy density are served, and one condition in which meals of higher energy density are served. The order of conditions across the three 5-day periods will be counterbalanced across classrooms. Children will be served the same amount (weight) of food and beverages across all three conditions. In the lower-ED condition, the amount of energy served over each day is ~225 calories less than in the baseline condition. Energy served over the day in the higher-ED condition is ~225 calories more than in the baseline condition. Daily menus in all conditions meet the minimum guidelines for energy and food groups outlined by the USDA and the Child and Adult Care Food Program (CACFP).

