6.2 Study Procedures

1. Over 5 consecutive days, enrolled children will be served breakfast, lunch, dinner, and snacks of foods commonly served in the child care center according to their regular meal and snack schedules. Study menus were developed from the menus at each child care center to be similar to the foods that children are regularly served. Milk or water will be served as beverages. Meals will be served at tables of 3 to 6 children and one adult, which is a standard practice at the child care centers. The adults at the table will be instructed not to discuss the food or to encourage the children to eat. There will be three experimental conditions, which differ only in food energy density. The lower-energy-density condition will provide foods 20% lower in energy density than the baseline condition, and the higher-energy-density condition will provide foods 20% higher in energy density than the baseline condition. Each participant will be served individual pre-weighed meals. All food and beverage items will be weighed with a food scale before and after meals to within 0.1 grams in order to determine the amount consumed. Participants will be told they can eat as much or as little of the foods as they would like. Trained study staff will document food and beverage spillage and any comments made about the food. The children will be provided with an evening snack pre-packaged for consumption at home. Any leftover food from the evening snack will be returned to the child care center the following day to be weighed.

2. Parents will be asked not to serve any additional food or beverages to their child apart from those provided by the study and water. If there is any deviation from this procedure, parents will be asked to report the extra food and beverage consumption.
3. Physical activity levels will be measured using tri-axial accelerometers worn over the five study days in each period. The accelerometers will be worn while the children are present at the child care center (from before breakfast to after dinner). Study staff will attach a device to the child's waist upon arrival at the center each morning and remove the device upon the child's departure from the center each evening.

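### A narrowing kcal gap between energy-density conditions is read as regulation, but a shared within-week change in grams of manipulated food eaten can produce or hide it

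*Combined protocol and SAP*

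**What the plan says.** Hypothesis 2 (section 1.1) is on the energy scale: "Daily energy intake in the conditions with higher and lower energy density will begin to converge across the 5-day period". The only primary endpoint (section 1.2) is also energy: "Daily intake of food and beverages by energy (kilocalories").

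Section 8.2 specifies random coefficients models with study day as a continuous covariate and linear and quadratic terms. Their purpose is to see whether the trajectories "converge over the 5 days, i.e., whether regulation of energy intake occurs over time in response to ED variations". Convergence and regulation are thus treated as the same thing. That paragraph refers to daily intake without naming a scale.

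On the design, section 6.1 fixes the weight served across conditions. Section 6.2 sets "foods 20% lower in energy density than the baseline condition" and "foods 20% higher in energy density than the baseline condition". In energy terms, section 6.1 says that in the lower-ED condition "the amount of energy served over each day is ~225 calories less than in the baseline condition", and "Energy served over the day in the higher-ED condition is ~225 calories more than in the baseline condition".

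Section 8.1 gives the sizing target: "To detect a clinically significant change of 50 kcal/d over time", with 5% Type 1 error, 90% power and 45 children.

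Section 8.2 also lists weight and ED among the main outcomes, separately for manipulated foods and for non-manipulated foods and milk. In the models for mean daily outcomes it tests interactions among the fixed factors, which include condition and study day.

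**The concern.** The manipulation is multiplicative: the same grams carry more or fewer kilocalories. Any day-to-day change in grams of manipulated food that all conditions share is therefore larger in kcal in the higher-ED week than in the lower-ED week. In a kcal model it appears as a condition-by-day term, which is the term that Hypothesis 2 examines. A main effect of day cannot absorb it. Counterbalancing the order of whole periods does not remove it either, because the drift occurs inside each period. Quadratic terms are affected in the same way.

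Convergence across the days of a period is the question on which the trial was sized. If children tire of the study meals as the week goes on, the kcal gap closes and the plan's wording would call that regulation. If they warm to the meals, the gap opens and could conceal real adjustment.

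**Working it through.** **Inputs from the documents.** ED at −20% and +20% of baseline (6.2); about −225 and +225 kcal/d served (6.1), hence 225 + 225 = 450 kcal/d between higher and lower; equal weight served (6.1); target 50 kcal/d, 5% error, 90% power, 45 children (8.1).

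**Not in the documents, so assumed.** Fraction of manipulated food eaten (70%, range 60–80%); size of any shared drift; standard error; a two-sided test. The mix of manipulated foods eaten is taken as constant.

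**The plan's own figure.** The 45 cannot be reproduced, because section 8.1 gives no variance components. Back-solving a simple paired contrast gives SE = 50/(1.960 + 1.282) = 15.4 kcal, or a within-child SD of 15.4 × √45 ≈ 103.5 kcal. This assumes that the 50 kcal is the change in the higher-versus-lower gap.

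**Splitting the gap.** Let D be baseline ED and W_high, W_low the grams of manipulated food eaten, with mean M = (W_high + W_low)/2. Then

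E_high − E_low = 1.2·D·W_high − 0.8·D·W_low = 0.4·D·M + D·(W_high − W_low).

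The second term is the response to ED. The first moves with shared intake.

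**No response to ED.** With W_high = W_low and a fraction p eaten, the gap is 450·p: 270, 315 or 360 kcal at p = 0.6, 0.7 or 0.8 (as a check, 225/0.20 = 1125 kcal served at baseline, and 0.4 × 1125 = 450). The shared fall in p that mimics the target is

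- higher versus lower: 50/450 = 11.1 percentage points, a relative fall of 18.5%, 15.9% or 13.9% at p = 0.6, 0.7 or 0.8;
- one condition versus baseline: 50/225 = 22.2 points.

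**Rejection rate of a nominal 5% kcal test** (p = 0.7, SE 15.4, normal approximation, no regulation):

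| Shared relative fall, Day 1 to 5 | Narrowing, 315 × fall | Narrowing/SE | Rejects |
|---|---|---|---|
| 2% | 6.3 kcal | 0.41 | 7% |
| 5% | 15.75 kcal | 1.02 | 18% |
| 10% | 31.5 kcal | 2.04 | 53% |
| 15% | 47.25 kcal | 3.06 | 87% |

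For a 10% fall, the rate is 42% at p = 0.6 and 65% at p = 0.8.

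**Sensitivity to noise.** If the SE were twice as large (30.8 kcal), the ratios for 5%, 10% and 15% halve to 0.51, 1.02 and 1.53, and the rejection rates become about 8%, 18% and 33%. A one-condition-versus-baseline contrast at SE 15.4 gives the same figures, since its narrowing is half as large.

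**Simulation** (45 children, 4000 trials per setting, 70% eaten, noise set near the implied SE, per-child higher-minus-lower slope):

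- No regulation, shared falls of 5%, 10% and 15%: the kcal test rejects in 18%, 53% and 88%; the test on grams of manipulated food stays at about 5%.
- True adjustment worth 50 kcal, shared rises of 0%, 5%, 10% and 15%: kcal power is 86%, 59%, 28% and 9%; power on grams is 87–91%.

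**The case against.** The strongest reply is that the plan already measures what is needed. Weight of manipulated foods is a main outcome, the mean-intake models test interactions that include condition by day, and the trajectory paragraph does not confine itself to kcal. A reader might infer that the plan relies on kcal alone; the documents do not support that. What stands of the concern is narrower: nothing ties the word regulation to the weight result, so a kcal convergence could be reported as regulation whatever the grams show.

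A reader might also infer that any drift in amount eaten distorts Hypothesis 2. It does not. A drift confined to non-manipulated foods and milk leaves the kcal gap unchanged, and a 2% drift in manipulated foods matters little. Nor is the gap simply grams times a fixed ED difference: when grams differ between conditions, the second term is added, and that term is the signal.

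It is also fair to say that no section reports or predicts a drift of 10–15%, that section 8.1 does not say which contrast the 50 kcal refers to, and that the rejection rates depend on an implied SE. These points limit what can be said about size, but they leave the algebra intact. Hypothesis 3 is less exposed: with equal grams, a shared drift changes the higher-versus-baseline and baseline-versus-lower gaps equally.

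**Conclusion.** The point holds in a limited form. On the kcal scale, convergence is not by itself evidence of regulation, because a shared within-week change in grams of manipulated food produces the same condition-by-day pattern. The direction follows from the design figures alone. The size does not: it rests on the assumed fraction eaten, the assumed drift, the SE back-solved from 45 children, and the higher-versus-lower reading of the 50 kcal. Under those assumptions the inflation is slight at 2% drift and serious from about 10%; with noisier data it is smaller.

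The documents do not show that such a drift occurs. A reader might infer that the sample size is therefore wrong, but nothing here shows that 45 is in error. The gap is in the rule for interpretation, and it should be closed because the needed data are already collected.

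**What to change.** In section 8.2:

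1. Keep the kcal random coefficients model as the description of convergence.
2. Fit the same model (condition by day, linear and quadratic) to daily grams of manipulated foods, and to daily energy from non-manipulated foods and milk. The second is needed because a child may compensate through those items.
3. Conclude that regulation occurred only if at least one of these two shows a condition-specific change in the compensating direction, with the lower-ED condition rising relative to the higher-ED condition. Otherwise report kcal convergence as compatible with a common drift.
4. Do not use log total energy as the safeguard. It cancels a shared drift only if manipulated and non-manipulated items drift in the same proportion. A log analysis, if wanted, should be confined to manipulated foods.

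This builds on outcomes and interaction tests already planned and needs no new data. The cost is some extra analysis and a few sentences of SAP text, and kcal convergence alone can no longer be claimed as regulation. One limit remains: switching among manipulated items at the same total grams would not show in the gram model.

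### Does the convergence analysis need a stated time origin and a named higher-versus-lower contrast?

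*Combined protocol and SAP*

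**What the plan says.** Hypothesis 2 (section 1.1) expects daily energy intake in the higher- and lower-ED conditions to start coming together over the five days. Section 8.2 assigns the question to one analysis: "Random coefficients models are used to test whether the trajectories of daily intake in the 3 conditions converge over the 5 days". Study day enters as a continuous covariate, and "polynomial factors of time (linear and quadratic coefficients) are tested as both fixed and random effects to determine the shape of the intake trajectory". Each child has an individual curve: "The trajectories of intake over time are modeled separately for each child and allowed to vary randomly".

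The coefficients are then glossed. On the intercept: "The intercept of the trajectory reflects the magnitude of daily intake". On the linear term: "The linear coefficient represents the rate of change in intake (slope) across time after Day 1". On the quadratic: "the quadratic coefficient represents the rate of acceleration or deceleration in intake (curvature) across time after Day 1".

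Section 8.1 sized the study on change over time, using several scenarios with "different assumptions about changes in intake on days 3 to 5 that represented quadratic trajectories over time". The target was a 50 kcal/d change with 90% power and a 5% Type 1 error rate, which gave 45 children.

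A separate linear mixed model in section 8.2 compares mean daily intake between conditions. It lists ED condition and study day among its fixed factors and provides for testing the interactions between factors.

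**The concern.** Three things look incomplete. The zero point of time is implied by the references to Day 1 but never stated. The random coefficients paragraph names no condition-by-time term and no higher-minus-lower contrast. And if time is counted from Day 1 with the quadratic kept, two of the glosses are inexact: the intercept is fitted Day 1 intake, and the linear coefficient is the slope at Day 1, not an average over the later days.

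This concerns the question that set the sample size, and section 8.1 planned for curved paths, where the Day 1 slope and the change over the week differ. An analyst who took the linear coefficient as the measure of convergence could miss a gap that closes late. Analysts using different codings could report different linear terms from the same data.

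**Working it through.** **The plan's own figure.** The documents give no SD or covariance, so 45 cannot be reproduced. Back-solving for a within-child contrast, two-sided: SD = 50 × √45 / (1.960 + 1.282) = 103 kcal/d. This is not evidence against 45, and nothing below bears on it.

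**Coefficients under different codings.** Write the higher-minus-lower gap as b0 + b1·t + b2·t², with t = day − 1. The slope at time t is b1 + 2·b2·t, the average slope over Days 1 to 5 is b1 + 4·b2, and the Day 1 to Day 5 change is 4·b1 + 16·b2. In raw days 1 to 5 the linear term becomes b1 − 2·b2; with day − 3 it becomes b1 + 4·b2. The quadratic coefficient b2 is the same in all three.

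Assume that the gap closes from 150 to 100 kcal/d (section 8.1 does not say whether its 50 kcal/d is a gap or a within-condition change):

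| Path | b2 | Linear term, day − 1 | Raw day | Day − 3 | Mean gap |
|---|---|---|---|---|---|
| Linear | 0 | −12.5 | −12.5 | −12.5 | 125 |
| Accelerating | −3.125 | 0 | 0 + 6.25 = +6.25 | 0 − 12.5 = −12.5 | 131.25 |
| Decelerating | +3.125 | −25 | −25 − 6.25 = −31.25 | −25 + 12.5 = −12.5 | 118.75 |

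The Day 1 intercept is 150 in every row. So the point about wording is right: with curvature kept, the linear term depends on coding and, counted from Day 1, is not the average change. In each row the Day 1 to Day 5 change is −50 (accelerating: 4 × 0 + 16 × −3.125; decelerating: 4 × −25 + 16 × 3.125), so the fitted gap is the same whichever coding is used.

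**Power when both terms are read together.** Assume independent errors, and a scale at which the Day 1 to Day 5 contrast (variance 1.6σ²) has 90% power. Then σ, the SE of each day's mean gap, is 50 / (3.242 × √1.6) = 12.19 kcal. The joint 2-df test of the linear and quadratic terms has these noncentralities:

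- Linear path: 3.242² = 10.51, power 83.5%.
- Accelerating or decelerating path: 10.51 + 3.125² / (0.0714 × 12.19²) = 10.51 + 0.92 = 11.43, power 86.6%.

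The test does not change with the origin, and it is held at 5% when the gap is flat.

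**The rule that would do harm.** Suppose that the quadratic is tested, dropped if P > .05, and convergence then judged on the Day-1-coded linear term alone, even when the quadratic is significant. Convergence is then declared in 88.0% (linear), 75.8% (accelerating) and 91.4% (decelerating) of trials. With a flat gap, some change is declared in 8.4%. The shortfall on the accelerating path arises because the quadratic is kept in 16% of trials, and in those the linear term shows convergence in only 1.1%. The rule sets aside the very term that detected the closing. Section 8.2 contains no such rule.

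**The case for a change.** The strongest argument for a change is that convergence has a direction. The joint test shows that the gap changes, not that it closes, so some directional quantity has to be chosen. The only guidance on interpretation is a set of glosses that are inexact in the curved case for which the study was sized. Naming a contrast would take a few sentences, and leaving it open gives freedom after the data are seen.

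Part of this stands: no contrast is named, and the linear and intercept glosses are loose when the quadratic is kept. The rest carries less weight. Both slope glosses refer to time after Day 1, so day − 1 is the natural coding; raw days and day − 3 fit that wording poorly. The intercept wording affects no planned inference, because Hypothesis 1 is tested in the separate means model with Tukey-Kramer comparisons. An analyst who finds a significant joint test will look at the fitted gap by day, which gives the direction at once. The means model also provides for a condition-by-day interaction, though that test too has no direction.

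Nor is the obvious candidate clearly better. A Day 1 to Day 5 contrast has 90% power by construction here, but it would miss a gap that narrows in mid-week and rebounds, which the wording of Hypothesis 2 could include.

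**Conclusion.** No change to the plan is needed. The gap is real but small: an unwritten time coding and contrast that analysts would fill sensibly, plus loose descriptions of two coefficients. The model is valid, no stated figure is shown to be wrong, and 45 is unaffected. Reading the linear and quadratic condition-by-time terms together, with direction taken from the fitted higher-minus-lower gap, keeps 84% to 87% power at the nominal 5% level.

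The drop to 76% power and the 8.4% error rate belong to a linear-term-only rule that the plan does not state, so they are not evidence of harm. The power figures rest on independent errors, an assumed gap closing from 150 to 100 kcal/d, and a scale fixed at 90% power for the Day 1 to Day 5 contrast. The coding algebra needs none of these. The conclusion would differ if the plan made the linear coefficient alone decide Hypothesis 2; it does not.

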3.2 Exclusion Criteria

1. Children with allergies or restrictions to any of the foods served
2. Children with health issues that preclude participation
3. Children who are unavailable for the entire duration of the study

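### Does the t-test of intake between the ≥85 and <85 BMI-percentile groups need to be replaced by the mixed model, with energy need taken into account?

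*Combined protocol and SAP*

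**What the plan says.** In section 8.2 of the combined protocol and SAP, daily intake is compared across the three conditions by the main model: "linear mixed models with repeated measures are used", and "Participants are treated as a random effect". Classroom and sex are among its fixed factors.

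The same section then treats weight status in three ways.

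- Continuous body weight, BMI-for-age percentile and BMI z-score are covariates in linear mixed models, with false-discovery-rate control. "In order to standardize for energy needs, models having significant covariance with weight status are adjusted for estimated energy requirements".
- Two groups are formed at the 85th percentile, and "differences in intake between children with and without obesity (sex-specific BMI-for-age percentile ≥ 85" and above, versus below 85) "are assessed by independent-samples t-tests". The same sentence covers differences in subject characteristics between boys and girls.
- Within conditions, "the means of daily energy intakes expressed as a percentage of estimated energy requirements are compared to 100" percent by a one-sample test. This is not split by weight group.

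On missing data, section 8.2 removes only children with "incomplete intake measures on ≥ 3 days in all 3 conditions will be excluded from analysis". Section 3.2 already excludes "Children who are unavailable for the entire duration of the study".

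**The concern.** Three features look wrong at first.

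1. **Unit.** Intake is a daily measure, and section 6.3 gives each child three 5-day periods. A t-test on child-days would treat 15 correlated values per child as independent. The main model handles this correlation with a child effect; nothing in the text explicitly carries that over to the t-test.
2. **Energy need.** The plan recognises elsewhere that weight status and energy requirement are linked, yet its one explicit weight-group comparison of intake has no stated standardisation. A higher raw intake in the ≥85 group could simply reflect a higher requirement.
3. **Lost days.** A child who missed most or all of one condition is kept, and that child's simple mean is then not balanced over the three energy densities.

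At stake would be a false claim that heavier children ate more, or a true raw difference read as overeating relative to need.

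**Working it through.** **The plan's own figures.** The plan gives none for this contrast. Its sample size of 45 (section 8.1) is for a change of 50 kcal/d over time, with 5% error and 90% power. No SD is printed, so it cannot be reproduced. The simple normal formula for a within-child contrast implies an SD of 50 × √45 / (1.960 + 1.282) ≈ 103 kcal/d. That says nothing about a comparison between children.

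**1. Unit.** Assume an intraclass correlation (ICC) of 0.2 to 0.5 between days of one child. For m days per child, the design effect is DE = 1 + (m − 1) × ICC, and the type I error of a naive test is 2 × [1 − Φ(1.96/√DE)].

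| Unit | DE | Type I error |
|---|---|---|
| Child-days, m = 15 | 3.8 to 8.0 | 31% to 49% |
| Child-days, m = 5 (one condition) | 1.8 to 3.0 | 14% to 26% |
| One mean per child, simulated | – | 5.0% on average (3.0% to 6.8%) |
| Mixed model with group added, simulated | – | 5.0% on average (2.7% to 7.0%) |

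The simulated rows cover 48 settings of 600 runs with no true difference: 45 or 55 children, 15% or 30% in the ≥85 group, 6 classrooms assumed, and up to 20% of children losing 3 or 5 days of one condition. The Monte Carlo standard error is 0.9 points per setting. With 20% of children losing days, the child-mean test stands at 5.2%. A separate simulation with ICC 0.1 to 0.7 gives 4.6% to 5.5% for child means.

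The unit therefore matters, but the text points to the valid one. The sentence pairs this test with boy–girl characteristics, which have one value per child. The test is named for independent samples. The same section models days as repeated measures within a child.

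**2. What the mixed model would gain.** With C classrooms plus sex in the model, between-child degrees of freedom fall from N − 2 to N − C − 2. If classroom and sex explain nothing, chance overlap with the group factor inflates the variance by 1/[1 − C/(N − 1)]. Interval widths relative to the t-test, including the change in critical value:

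| C (assumed) | N = 45 | N = 55 |
|---|---|---|
| 3 | 1.04 | 1.03 |
| 6 | 1.08 | 1.06 |
| 9 | 1.13 | 1.10 |
| 12 | 1.19 | 1.14 |

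If classrooms do differ, the model can be tighter. The simulated SE ratio is 0.90 to 1.00 with a classroom SD of 0.3 of the day-level SD (6 classrooms), and 0.95 to 1.01 with a classroom SD of 100 kcal/d (5 or 9 classrooms). Adding energy requirement as a covariate correlated r with group multiplies the SE by 1/√(1 − r²), which is 1.05, 1.15 and 1.40 for r = 0.3, 0.5 and 0.7, unless the covariate explains enough variance to offset this.

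The contrast is imprecise either way. At 80% power the detectable difference is (1.96 + 0.84) × √(1/n₁ + 1/n₂) child-level SDs: 1.15 with 7 versus 38 children, 0.97 with 11 versus 34, and 0.79 with 19 versus 36 (group sizes assumed).

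**3. Energy need.** Sections 6.1 and 6.2 give about 225 kcal and 20%, so the altered foods supply roughly 225/0.20 = 1125 kcal/d at baseline. Suppose intake is proportional to need and the ≥85 group's requirement is 5% to 15% higher. If the <85 group eats half, a 5% gap gives 1125 × 0.5 × 0.05 = 28 kcal/d. At the other end nobody can eat more than is served, so a 15% gap gives at most 1125 × (1 − 1/1.15) = 147 kcal/d. Such a raw difference could arise with no difference relative to need. The range is illustrative: the proportionality and the 5% to 15% are assumptions.

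**4. Lost days.** Let the condition effects be −d, 0 and +d, with d = 112.5 to 225 kcal/d (50% to 100% of served weight eaten). A child with 2 of 5 lower-density days and all other days has a simple mean too high by (−2d + 5d)/12 = d/4 = 28 to 56 kcal/d; averaging within condition first makes this 0. With no lower-density day the excess is 5d/10 = d/2 = 56 to 112 kcal/d. In a group of 11 (25% of 45), one such child moves the group mean by 56/11 to 112/11, about 5 to 10 kcal/d. Losing higher-density days moves it the other way.

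**The case for a change.** The best case for a change is that the unit decides whether the test is valid, and a plan should not leave that to inference. The intake outcome is also left open: section 8.2 defines intake by weight, energy density and energy, for altered foods, unaltered foods and milk, and their total. The energy-need point has some force, because a gap of 28 to 147 kcal/d can be set beside the 50 kcal/d that section 8.1 calls clinically significant. The existing adjustment is conditional on a significant covariance, and it belongs to models of how child characteristics bear on the effect of condition, so it does not directly answer whether the ≥85 group ate more relative to need. Stating the unit and adding a percentage-of-requirement version would need no new data.

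What stands is that the text is incomplete on unit and scale. What does not stand is that this makes the analysis wrong. A raw difference in intake is a legitimate question in its own right, and because the plan does not name the scale, it cannot be said to rule out the percentage-of-requirement version. The 50 kcal/d target is a change over time within children, not a difference between groups. Swapping a valid t-test for a model of equal validity and uncertain precision is a preference.

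**Conclusion.** No change to the plan follows. The missing unit is a gap that an analyst fills in the obvious way, with one mean per child, or one per child within a condition. On the first, type I error is about 5% across every range tried, including with lost days. The large error rates belong to a child-day reading that nothing in the text supports. Moving the contrast into the mixed model leaves validity unchanged and alters the interval by anything from about 10% narrower to 19% wider, before any price for an energy-requirement covariate. The lost-days effect is about 5 to 10 kcal/d in a group mean per affected child. It biases the comparison only if losses differ between the groups, and section 3.2 should keep such children few.

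This rests on the one-mean-per-child reading and on assumed values for the ICC, the share of children in the ≥85 group, the number of classrooms and the link between requirement and weight group, none of which the documents give. A reader of the results should take a raw difference between the groups as just that, and look to the covariate models for weight status and energy need. The hypotheses, primary endpoint and sample size are untouched.
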